4.3 Exclusion Criteria

The presence of any of the following will exclude a subject from randomization (with the randomization date defined as the date in which the subject is randomized in IRT):

1) Subject with the any of the following prior treatments:

- Erythropoiesis-stimulating agents (ESAs)
 - Subjects may be randomized at the investigator’s discretion contingent on the fact that the subject received no more than 2 doses of epoetin alfa (prior treatment with darbepoetin not acceptable for entry into the study). The last dose of epoetin alfa must be ≥ 8 weeks from the date of randomization. A blood sample to determine the endogenous sEPO level (central laboratory) for stratification must be taken within 5 days of randomization unless a prior screening sample analyzed by the central laboratory demonstrated an endogenous sEPO level ≤ 500 U/L.
- Granulocyte colony-stimulating factor (G-CSF), granulocyte-macrophage colony-stimulating factor (GM-CSF), within 8 weeks prior to randomization, unless given for treatment of febrile neutropenia
- Disease modifying agents (eg, immune-modulatory drug [IMiDs such as lenalidomide])
 - Except if the subject received ≤ 1 week of treatment with a disease modifying agent ≥ 8 weeks from randomization, at the investigator’s discretion.
- Hypomethylating agents
 - Subjects may be randomized at the investigator’s discretion contingent that the subject received no more than 2 doses of HMA. The last dose must be ≥ 8 weeks from the date of randomization.

¹ True abstinence is acceptable when this is in line with the preferred and usual lifestyle of the subject. [Periodic abstinence (eg, calendar, ovulation, symptothermal, post-ovulation methods) and withdrawal are not acceptable methods of contraception].

² Highly effective contraception is defined in this protocol as the following (information will also appear in the ICF): Hormonal contraception (for example, birth control pills, injection, implant, transdermal patch, vaginal ring); intrauterine device (IUD); tubal ligation (tying your tubes); or a partner with a successful vasectomy.

- Luspatercept (ACE-536) or sotatercept (ACE-011)
 - Immunosuppressive therapy for MDS
 - Hematopoietic cell transplant
- 2) Subject with MDS associated with del(5q) cytogenetic abnormality or MDS unclassifiable (MDS-U) according to WHO 2016 classification.
 - 3) Subject with myelodysplastic/myeloproliferative neoplasms (MDS/MPN) according to WHO 2016 classification (ie, Chronic myelomonocytic leukemia (CMML), Atypical chronic myeloid leukemia (aCML), BCR-ABL12, Juvenile myelomonocytic leukemia (JMML), MDS/MPN unclassifiable).
 - 4) Subject with secondary MDS, ie, MDS that is known to have arisen as the result of chemical injury or treatment with chemotherapy and/or radiation for other diseases.
 - 5) Subject with known clinically significant anemia due to iron, vitamin B12, or folate deficiencies, or autoimmune or hereditary hemolytic anemia, or hypothyroidism, or any type of known clinically significant bleeding or sequestration. Subject with drug induced anemia (eg, mycophenolate).
 - Iron deficiency to be determined by serum ferritin < 100 µg/L and additional testing if clinically indicated (eg, calculated transferrin saturation [iron/total iron binding capacity ≤ 20%] or bone marrow aspirate stain for iron).
 - 6) Subject with known history of diagnosis of AML.
 - 7) Subject receiving any of the following treatment within 8 weeks prior to randomization:
 - Anticancer cytotoxic chemotherapeutic agent or treatment
 - Systemic corticosteroid, except for subjects on a stable or decreasing dose for ≥ 1 week prior to randomization for medical conditions other than MDS
 - Iron-chelating agents, except for subjects on a stable or decreasing dose for at least 8 weeks prior to randomization
 - Other RBC hematopoietic growth factors (eg, Interleukin-3)
 - Androgens, unless to treat hypogonadism
 - Hydroxyurea
 - Oral retinoids (except for topical retinoids)
 - Arsenic trioxide
 - Interferon and interleukins
 - Investigational drug or device, or approved therapy for investigational use (if 5 times the half-life of the previous investigational drug exceeds 8 weeks, then the time of exclusion should be extended up to 5 times the half-life of the investigational drug)
 - 8) Subject with uncontrolled hypertension, defined as repeated elevations of systolic blood pressure (SBP) of ≥ 150 mmHg and/or diastolic blood pressure (DBP) ≥ 100 mmHg despite adequate treatment.
 - 9) Subject with any of the following laboratory abnormalities:
 - Absolute neutrophil count (ANC) < 500/µL (0.5 x 10⁹/L)
 - Platelet count < 50,000/µL (50 x 10⁹/L)

- Estimated glomerular filtration rate (eGFR) < 40 mL/min/1.73 m² ([APPENDIX F](#))
 - Serum aspartate aminotransferase/serum glutamic oxaloacetic transaminase (AST/SGOT) or alanine aminotransferase/serum glutamic pyruvic transaminase (ALT/SGPT) ≥ 3.0 x upper limit of normal (ULN)
 - Total bilirubin ≥ 2.0 x ULN.
 - Higher levels are acceptable if these can be attributed to active red blood cell precursor destruction within the bone marrow (ie, ineffective erythropoiesis) or in the presence of known history of Gilbert Syndrome.
- 10) Subject with prior history of malignancies, other than MDS, unless the subject has been free of the disease for ≥ 5 years. However, subjects with the following history/concurrent conditions are allowed:
- Basal or squamous cell carcinoma of the skin
 - Carcinoma in situ of the cervix
 - Carcinoma in situ of the breast
 - Incidental histologic finding of prostate cancer (T1a or T1b using the tumor, nodes, metastasis [TNM] clinical staging system)
- 11) Subject with major surgery within 8 weeks prior to randomization. Subjects must have completely recovered from any previous surgery prior to randomization.
- 12) Subject with history of cerebrovascular accident (including ischemic, embolic, and hemorrhagic cerebrovascular accident), transient ischemic attack, deep venous thrombosis (DVT; including proximal and distal), pulmonary or arterial embolism, arterial thrombosis or other venous thrombosis within 6 months prior to randomization
Note: prior superficial thrombophlebitis is not an exclusion criterion.
- 13) New-onset seizures or poorly controlled seizures within 12 weeks prior to randomization.
- 14) Subject with the following cardiac conditions within 6 months prior to randomization: myocardial infarction, uncontrolled angina, acute decompensated cardiac failure or New York Heart Association (NYHA) Class III-IV heart failure, or uncontrolled cardiac arrhythmia as determined by the investigator. Subjects with a known ejection fraction < 35%, confirmed by a local echocardiogram (ECHO) or multi-gated acquisition (MUGA) scan performed within 6 months prior to randomization.
- 15) Subject with uncontrolled systemic fungal, bacterial, or viral infection (defined as ongoing signs/symptoms related to the infection without improvement despite appropriate antibiotics, antiviral therapy, and/or other treatment).
- 16) Subject with known human immunodeficiency virus (HIV), known evidence of active infectious Hepatitis B, and/or known evidence of active Hepatitis C. Local laboratory testing confirming HIV, Hepatitis B, and Hepatitis C status should not have been performed beyond 4 weeks prior to the date of ICF signature.
- 17) Subject with history of severe allergic or anaphylactic reactions or hypersensitivity to recombinant proteins or excipients in luspatercept (see Investigator's Brochure).
- 18) Subject with known hypersensitivity to the active substance or to any of the excipients in epoetin alfa.
- 19) Subject with history of pure red cell aplasia (PRCA) and/or antibody against erythropoietin.

- 20) Female subject who is pregnant or breastfeeding.
- 21) Subject has any significant medical condition, laboratory abnormality, psychiatric illness, or is considered vulnerable by local regulations (eg, imprisoned or institutionalized) that would prevent the subject from participating in the study.
- 22) Subject has any condition including the presence of laboratory abnormalities, which places the subject at unacceptable risk if he/she were to participate in the study.
- 23) Subject has any condition or receives concomitant medication that confounds the ability to interpret data from the study.
- 24) Subject has history of active SARS-CoV-2 infection within 4 weeks prior to screening, unless the subject has adequately recovered from COVID symptoms and related complications as per investigator's discretion and following a discussion with the Medical Monitor. Use of a live COVID-19 vaccine is prohibited within 4 weeks prior to randomization.

5 TABLE OF EVENTS

Table 3: Table of Events

	Section	Screening Day -35 to Random-ization	Treatment Period (open-label)								Post-treatment Follow-up			
			W1D1 Visit ^c	W2D1 Visit	W3D1 Visit	Add. Visits EPO W5/6D1 W8/9D1 etc.	3-wkly Visits W4D1 W7D1 W10D1 etc.	Efficacy Assessment Independent of any dose delays		EOT Visit ^a	42-Day Follow-up	Long Term Follow-up	End of Study	
								24-Wk MDS Assessment Visit D169	Every 24 wks D337 D505 etc.					
Section								6.4	6.4	6.2.2/11.1	6.3.1	6.3.2	11.2	
Time window				±2 days	±2 days	±2 days	±2 days	±14 days ^b	±14 days ^b		+3 days	±7 days		

Note: Weekly visits as displayed above represent visits as they are scheduled if dosing occurs without any dose delays. In the event of dose delays (eg, due to adverse events) the next dosing visit (weekly for epoetin alfa and every three weeks for luspatercept) and associated assessments should be delayed accordingly. Assessments to monitor the condition of the subject should be recorded as unscheduled visits. Please note that efficacy assessments (MDS Disease assessments) always occur at the designated days after randomization as indicated above. Dose delays do not affect the timing of these assessments.
														
Informed Consent	6.1	X	-	-	-	-	-	-	-	-	-	-	-	-
Inclusion/Exclusion Evaluation	6.1	X	-	-	-	-	-	-	-	-	-	-	-	-
Physical Examination	6.1.5	X	-	-	-	-	-	X	X	X	-	-	-	-
Demographics	6.1.3	X	-	-	-	-	-	-	-	-	-	-	-	-
Medical History	6.1.4	X	-	-	-	-	-	-	-	-	-	-	-	-
HIV and Hep B/C Status	6.1.4.1	X	-	-	-	-	-	-	-	-	-	-	-	-
Prior RBC and Platelet Transfusions	6.1.2	X	-	-	-	-	-	-	-	-	-	-	-	-
Randomization ^c	6.1/9.4	X	-	-	-	-	-	-	-	-	-	-	-	-

Table 3: Table of Events

	Section	Screening Day -35 to Random- ization	Treatment Period (open-label)								Post-treatment Follow-up		
			W1D1 Visit ^c	W2D1 Visit	W3D1 Visit	Add. Visits EPO W5/6D1 W8/9D1 etc.	3-wkly Visits W4D1 W7D1 W10D1 etc.	Efficacy Assessment Independent of any dose delays		EOT Visit ^a	42-Day Follow- up	Long Term Follow- up	End of Study
								24-Wk MDS Assess- ment Visit D169	Every 24 wks D337 D505 etc.				
Section								6.4	6.4	6.2.2/11.1	6.3.1	6.3.2	11.2
Time window				±2 days	±2 days	±2 days	±2 days	±14 days ^b	±14 days ^b		+3 days	±7 days	
INVESTIGATIONAL PRODUCT (IP)													
IP Administration and Accountability Luspatercept	7	-	X	-	-	-	X	-	-	-	-	-	-
IP Administration and Accountability Epoetin alfa ^b	7	-	X	X	X	X ^d	X	-	-	-	-	-	-
SAFETY ASSESSMENTS													
ECOG Performance Status	6.1.7	X	X	-	-	-	X	X	X	X	-	-	-
Urinalysis	6.1.13	X	X	-	-	-	Every 12 weeks ie, W13D1 W25D1 etc.	-	-	-	-	-	-
ECG (12-lead)	6.1.8	X	-	-	-	-	-	-	-	-	-	-	-
Pregnancy Test and Counseling ⁱ	6.1.14	X	X	-	-	-	X	-	-	X	X	X ^k	-
Adverse events	6.1.18 10	Continuous, after signing informed consent until 42 days after last IP administration										-	-

Table 3: Table of Events

	Section	Screening Day -35 to Random-ization	Treatment Period (open-label)								Post-treatment Follow-up		
			W1D1 Visit ^c	W2D1 Visit	W3D1 Visit	Add. Visits EPO W5/6D1 W8/9D1 etc.	3-wkly Visits W4D1 W7D1 W10D1 etc.	Efficacy Assessment Independent of any dose delays		EOT Visit ^a	42-Day Follow-up	Long Term Follow-up	End of Study
								24-Wk MDS Assessment Visit D169	Every 24 wks D337 D505 etc.				
Section								6.4	6.4	6.2.2/11.1	6.3.1	6.3.2	11.2
Time window				±2 days	±2 days	±2 days	±2 days	±14 days ^b	±14 days ^b		+3 days	±7 days	
Prior and Concomitant medications/ procedures	6.1.17 8	Continuous, 8 weeks prior to randomization until 42 days after last IP administration or until the EOT visit, whichever occurs later									-	-	
Vital Signs (Height to be measured only at screening)	6.1.6	X	X	X	X	X ^d blood pressure only	X	X	X	X	-	-	-
Serum Chemistry	6.1.10	X	X	-	-	-	X	X	X	X	-	-	-
EFFICACY ASSESSMENTS													
Hematology	6.1.9	X	X	X	X	X ^d local Hgb only	X	X	X	X	-	-	-
Serum EPO	6.1.11	X	-	-	-	-	Every 6 weeks, ie, W7D1 W13D1 etc.	X	X	X	-	-	-
Serum Ferritin and other iron-related markers	6.1.12	X	X	-	-	-	X	X	X	X	-	-	-

Table 3: Table of Events

	Section	Screening Day -35 to Random-ization	Treatment Period (open-label)								Post-treatment Follow-up		
			W1D1 Visit ^c	W2D1 Visit	W3D1 Visit	Add. Visits EPO W5/6D1 W8/9D1 etc.	3-wkly Visits W4D1 W7D1 W10D1 etc.	24-Wk MDS Assessment Visit D169	Every 24 wks D337 D505 etc.	EOT Visit ^a	42-Day Follow-up	Long Term Follow-up	End of Study
Section								6.4	6.4	6.2.2/11.1	6.3.1	6.3.2	11.2
Time window				±2 days	±2 days	±2 days	±2 days	±14 days ^b	±14 days ^b		+3 days	±7 days	
Transfusion Data Collection and Assessment	6.1.2 6.4.1	Assess and record on ongoing basis (prior to each dose of IP) until 8 weeks after last dose of IP or the EOT Visit, whichever occurs later. Clinical site staff must confirm (and document in the subject’s source record) if any transfusions were received by the subject (including any transfusions received at institutions outside of the study site in between study visits) prior to each IP administration. In addition to local procedures in place at the site to capture this information, a patient transfusion diary will be provided to subjects and will be reviewed by the site when/if returned by the patient.										–	
MDS Disease Assessment	6.4.2	–	–	–	–	–	–	X	X		–	–	–
BMA and PB for Cytomorphology and Cytogenetic testing (including RS status) ^e	6.1.1	X	–	–	–	–	–	X	X	X	–	–	–
EXPLORATORY/BIOMARKER ASSESSMENTS													
PB for Exploratory Biomarkers (eg, TGF-β superfamily, MDS-associated molecular mutations and other markers of drug MOA)	6.1.1 6.7	X	–	–	X	–	W10D1 W34D1 only	X	X	X	–	–	–

Table 3: Table of Events

	Section	Screening Day -35 to Random-ization	Treatment Period (open-label)								Post-treatment Follow-up		
			W1D1 Visit ^c	W2D1 Visit	W3D1 Visit	Add. Visits EPO W5/6D1 W8/9D1 etc.	3-wkly Visits W4D1 W7D1 W10D1 etc.	Efficacy Assessment Independent of any dose delays		EOT Visit ^a	42-Day Follow-up	Long Term Follow-up	End of Study
								24-Wk MDS Assessment Visit D169	Every 24 wks D337 D505 etc.				
Section								6.4	6.4	6.2.2/11.1	6.3.1	6.3.2	11.2
Time window				±2 days	±2 days	±2 days	±2 days	±14 days ^b	±14 days ^b		+3 days	±7 days	
BMA for Exploratory Biomarkers (eg, soluble biomarkers, MDS-associated molecular mutations, erythroid differentiation and other markers of drug MOA) ^f	6.1.1 6.7	X	-	-	-	-	-	X	X	X	-	-	-
SARS-CoV-2 serology	6.7	X	-	-	-	-	-	X	D337 only	X	-	-	-
PK/ADA ASSESSMENTS													
PK Sample Collection (Luspatercept arm only) Should be collected prior to IP dosing on a dosing day	6.5	-	X	X	X	-	W4D1 W10D1 W16D1 W22D1 only	X	And every 12 weeks (± 14 days) from the 24-Week MDS Assessment visit for up to one year from the first dose. Once a subject has been discontinued from treatment, PK samples may no longer be collected as long as ADA are not detectable.			-	

Table 3: Table of Events

	Section	Screening Day -35 to Random-ization	Treatment Period (open-label)								Post-treatment Follow-up			
			W1D1 Visit ^c	W2D1 Visit	W3D1 Visit	Add. Visits EPO W5/6D1 W8/9D1 etc.	3-wkly Visits W4D1 W7D1 W10D1 etc.	Efficacy Assessment Independent of any dose delays		EOT Visit ^a	42-Day Follow-up	Long Term Follow-up	End of Study	
								24-Wk MDS Assessment Visit D169	Every 24 wks D337 D505 etc.					
Section								6.4	6.4	6.2.2/11.1	6.3.1	6.3.2	11.2	
Time window				±2 days	±2 days	±2 days	±2 days	±14 days ^b	±14 days ^b		+3 days	±7 days		
ADA Sample Collection (Luspatercept arm only) Should be collected prior to IP dosing on a dosing day	6.6	–	X	–	–	–	–	W4D1 W10D1 W16D1 W22D1 only	X	And every 12 weeks (±14 days) from the 24-Week MDS Assessment visit for up to one year from the first dose. If the subject was discontinued from study treatment earlier than one year from the first dose, additional samples will be collected if last ADA is positive.			–	
QUALITY-OF-LIFE														
EORTC QLQ-C30 ^g	6.8	X	X	–	–	–	–	X 6-wkly only W7D1 W13D1 etc.	X	X D337 only	X	–	–	–
FACT-An ^g	6.8	X	X	X	X	–	–	X	X	X D337 only	X	–	–	–
QUALMS-p ^g	6.8	X	–	–	–	–	–	–	X	–	–	–	–	–

Table 3: Table of Events

	Section	Screening Day -35 to Random-ization	Treatment Period (open-label)								Post-treatment Follow-up		
			W1D1 Visit ^c	W2D1 Visit	W3D1 Visit	Add. Visits EPO W5/6D1 W8/9D1 etc.	3-wkly Visits W4D1 W7D1 W10D1 etc.	Efficacy Assessment Independent of any dose delays	24-Wk MDS Assessment Visit D169	Every 24 wks D337 D505 etc.	EOT Visit ^a	42-Day Follow-up	Long Term Follow-up
Section								6.4	6.4	6.2.2/11.1	6.3.1	6.3.2	11.2
Time window				±2 days	±2 days	±2 days	±2 days	±14 days ^b	±14 days ^b		+3 days	±7 days	
Patient Treatment Satisfaction Survey ^g	6.8	X	X	-	-	-	6-wkly only W7D1 W13D1 etc.	X	X D337 only	X	-	-	-
Healthcare Resource Utilization	6.9	After signing ICF and until 42 days after the last IP dose or End of Treatment Visit, whichever period is longer									-	-	
FOLLOW-UP													
Monitoring for progression to AML and other malignancies/pre-malignancies	6.1.19 6.3.2 10.5	After signing ICF and until 5 years from the first dose of IP, or 3 years from the last dose (whichever occurs later), or until death, lost to follow-up, withdrawal of consent for further data collection											
Post-treatment MDS therapies	6.3.2	-	-	-	-	-	-	-	-	-	X	X	X
Survival Follow-up	6.3.2	-	-	-	-	-	-	-	-	-	X	X	X

Abbreviations: ADA = antidrug antibodies; AML = acute myeloid leukemia; BMA = bone marrow aspirate; BMB = bone marrow biopsy; D = Day; ECG = electrocardiogram; ECOG = Eastern Cooperative Oncology Group; EORTC QLQ-C30 = European Organization for Research and Treatment of Cancer Quality-of-Life Questionnaire; EOT = End of Treatment; EPO = erythropoietin; FACT-An = Functional Assessment of Cancer Therapy – Anemia; FCBP = female of childbearing potential; Hep = hepatitis; Hgb = hemoglobin; HIV = human immunodeficiency virus; ICF = informed consent form; IP = investigational product; IRT = integrated response technology; MDS = myelodysplastic syndromes; MOA = mechanism of action; PB = peripheral blood; PK = pharmacokinetics; QUALMS-P = Quality of Life in Myelodysplasia Scale - Physical Burden; RBC = red blood cell; SARS-CoV-2 = Severe acute respiratory syndrome coronavirus 2; TGF-β = transforming growth factor-beta; W/wk = week; wkly = weekly.

- ^a End of Treatment (EOT) Visit procedures/assessments may not need to be repeated if previously performed within ± 7 days of EOT Visit. If a subject is discontinued during a regular scheduled visit, all EOT procedures should be completed at that visit. End of Treatment (EOT) Visit procedures/assessments may occur at 42-Day Follow-up assessment if subject is discontinued within ± 7 days of 42 Day Follow-up assessment.
- ^b As central laboratory results from bone marrow and peripheral blood samples (ie, cytomorphology, cytogenetic analysis) are required as part of the MDS Disease Assessment, a 14-day window is allowed for the 24-Week MDS Disease Assessment Visit (ie, Day 169 \pm 14 days) in order to account for sample collection and turnaround time of results. Please see [Section 6.4.2](#) for details.
- ^c Randomization via IRT. The first dose of IP should be administered after, but within 3 days of randomization and can be on the same day as randomization.
- ^d On days where subject dosing occurs at home (if in line with local practice) and not at the site: blood pressure measurement and Hgb value collection are not applicable ([Section 7.2.2](#)).
- ^e Collection of a BMB is only required when adequate aspirate is not attainable. To allow for cytomorphology assessment and cytogenetic analysis of the BMB please follow guidance for processing the sample provided in the study's Central Laboratory Manual.
- ^f Remaining BMA (after quantity sufficient is allocated towards cytomorphology and cytogenetics analysis) will be used for exploratory biomarker studies. An additional bone marrow procedure should not be performed for these samples. Refer to the central laboratory manual for additional information related to sample collection.
- ^g Questionnaires should be completed by the subject prior to IP administration.
- ^h In the event epoetin alfa will be home-administered, compliance will be monitored using a medication diary card or other local procedures in place at the investigational site.
- ⁱ In the event of dose delays, counseling about pregnancy precautions and the potential risks of fetal exposure must be conducted monthly.
- ^k An additional pregnancy test is to be performed 12 weeks (± 7 days) from the date of last dose of IP for FCBP.

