6.4 Efficacy Assessment

Treatment response will be assessed locally by the investigator in accordance with IWG 2006 criteria for MDS (Cheson, 2006) (APPENDIX D), through assessment of administered RBC transfusions, hematology parameters, peripheral blood smears, bone marrow aspirates and/or biopsies, and cytogenetics. Central lab, cytomorphology and cytogenetics results will be used for response assessment. Please refer to Section 6.4.1 and Section 6.4.2 below for details.

Other efficacy assessments will include health-related quality-of-life, healthcare resource utilization.

The timing of efficacy assessments (MDS disease assessments, health-related quality-of-life, and healthcare resource utilization) as well as associated sampling and assessments (ie, bone marrow and peripheral blood samples, RBC transfusion assessment) are specified in the Table of Events (Table 3). Please refer to Section 6.1.1 for details on bone marrow aspirate samples for assessing treatment response.

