9.10 Other Topics

9.10.1 Health-related Quality-of-life Assessment

The effect of luspatercept and epoetin alfa on patients' HRQoL based on EORTC QLQ-C30, FACT-An, QUALMS-P and the Patient Treatment Satisfaction Survey will be assessed. The intent is to summarize the descriptive statistics of observed score at each visit and change from baseline at each post-baseline visit for all domains of the QLQ-C30 and FACT-An, QUALMS-P for each treatment group. Within-treatment and between-treatment differences will be examined using a 1-sample, 2-sided t-test and a pooled 2-sample, 2-sided t-test, respectively. However, these t-tests will be descriptive (ie, non-inferential) in nature.

In addition, the least square (LS) mean (95% confidence interval [CI] and p-value) for change from baseline at each post-baseline visit for all domains within each treatment group, and the difference in the LS means (95% CI, p-value) between treatment groups at each post-baseline visit, will be

estimated using the analysis of covariance (ANCOVA) model adjusting for baseline domain scores and stratification factors (ie, transfusion burden, RS status and sEPO level) where appropriate. Various schemes will be assessed for missing data imputation. Full details will be included in an HRQoL SAP.

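### Interim FACT-An and QLQ-C30 questionnaires shift with dose delays while Day 169 and Day 337 stay fixed, and the protocol conflicts on whether quality of life is exempt

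*Combined protocol and SAP*

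**What the plan says.** The note at the head of Table 3 (Section 5) covers dose delays. It says that "the next dosing visit (weekly for epoetin alfa and every three weeks for luspatercept) and associated assessments should be delayed accordingly". Checks made in the meantime are handled separately: "Assessments to monitor the condition of the subject should be recorded as unscheduled visits". The exemption reads: "Please note that efficacy assessments (MDS Disease assessments) always occur at the designated days after randomization as indicated above".

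Table 3 places FACT-An at W1D1, W2D1, W3D1 and every 3-weekly visit. QLQ-C30 is at W1D1 and then "6-wkly only W7D1 W13D1 etc". Footnote g ties both to dosing: "Questionnaires should be completed by the subject prior to IP administration". Both are also marked at Day 169 and Day 337, in columns headed "Independent of any dose delays", and at End of Treatment.

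Section 6.4 groups quality of life with the efficacy assessments: "The timing of efficacy assessments (MDS disease assessments, health-related quality-of-life, and healthcare resource utilization". Section 9.10.1 plans summaries, t-tests and ANCOVA estimates of "change from baseline at each post-baseline visit for all domains within each treatment group", with the between-arm difference at each visit. It leaves full details to a separate HRQoL SAP, which is not among the documents.

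**The concern.** The rules that end a delay depend on the subject's condition. In Tables 5 and 7, a delay for a suspected related adverse event of Grade 3 or higher ends at Grade 1 or lower, or baseline. A delay for predose hemoglobin of 12.0 g/dL or more ends below 11.0 g/dL. If the questionnaire waits for the resumed dosing visit, it is completed after that condition has eased. It also keeps a visit label that no longer matches the study day.

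Health-related quality of life is a named secondary objective, with a timeframe of screening through Week 24 (Table 2). At stake is whether a by-visit comparison describes the two arms at a common time, and whether subjects in a delay are sampled at all. A later analysis can re-assign a late questionnaire to the right study day. It cannot recover one that was not completed on the scheduled day.

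**Working it through.** The plan states no figure on this point, so there is none to reproduce. The check is a reading of the schedule plus day arithmetic.

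**Which assessments move.**
- FACT-An has 9 post-baseline visits before Day 169: W2D1, W3D1, W4D1, W7D1, W10D1, W13D1, W16D1, W19D1 and W22D1.
- QLQ-C30 has 3: W7D1, W13D1 and W19D1.
- From W4D1 on, these are dosing visits in both arms, so the Table 3 note moves them.
- W2D1 and W3D1 are dosing visits for epoetin alfa only. A luspatercept delay does not clearly move them.
- Day 169 does not move. Section 6.4.2 sets it at 24 calendar weeks after first dose: 24 × 7 + 1 = 169. Day 337 is likewise 48 × 7 + 1 = 337.

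**Nominal days.** Day of WnD1 = 7(n − 1) + 1. This gives W4D1 = 22, W7D1 = 43, W10D1 = 64, W13D1 = 85, W16D1 = 106, W19D1 = 127 and W22D1 = 148.

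**Effect of one delay.** Suppose one delay of D weeks starts at W7D1 and there are no others. Each later dosing visit then falls on its nominal day + 7D. The documents give no delay lengths, so D is an assumed range. Its upper end, 12 weeks, is the limit that footnote c of Tables 5 and 7 attaches to the adverse-event row.

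| Assumed delay | W7D1 on day | W22D1 on day | Gap from W4D1 to next FACT-An | FACT-An W7D1–W22D1 done by Day 169 | QLQ-C30 done by Day 169 |
|---|---|---|---|---|---|
| 1 week | 50 | 155 | 4 weeks | 6 of 6 | 3 of 3 |
| 3 weeks | 64 | 169 | 6 weeks | 6 of 6 | 3 of 3 |
| 6 weeks | 85 | 190 | 9 weeks | 5 of 6 | 3 of 3 |
| 12 weeks | 127 | 232 | 15 weeks | 3 of 6 | 2 of 3 |

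For the 6-week row: 43 + 42 = 85, the nominal day of W13D1; and 148 + 42 = 190. Day 190 is beyond Day 169 and its ±14-day window (days 155 to 183), so W22D1 comes after the visit it should precede. The planned FACT-An gap at that point is 3 weeks.

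**The two texts side by side.** The Table 3 note exempts efficacy assessments but names only the MDS disease assessments in its parenthesis. Section 6.4 counts quality of life as an efficacy assessment, then refers back to Table 3 for its timing. Table 3 lists the questionnaires under a quality-of-life heading, apart from its efficacy block. A site could reasonably follow either reading.

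**The case against.** Several counter-arguments have force.

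- **The anchor points are fixed.** Day 169, which closes the Week 24 timeframe, and Day 337 do not move, and End of Treatment captures subjects who stop. This stands. The point concerns interim visits only.
- **The state that triggers a delay may still be captured.** Tables 5 and 7 assess the trigger predose at an attended visit, and nothing forbids completing the questionnaire there. Every 3-weekly luspatercept dosing visit is also a FACT-An visit. A reader might infer that high-hemoglobin or toxicity periods are systematically removed; the documents do not establish that. The argument is incomplete, however. QLQ-C30 is due only at every second 3-weekly visit, and the in-between epoetin alfa visits (such as W5D1) carry no questionnaire. Nor does the text say whether a form completed at the triggering visit counts as that visit's form.
- **The HRQoL SAP may define windows.** Section 9.2 also leaves time windows to the SAP. Windows could correct the labels, but not supply missing forms.
- **Arm differences are unproven.** A reader might infer that weekly dosing makes epoetin alfa visits drift more. That follows only from assuming an equal delay chance per dosing visit. With 2% per visit (assumed), expected delays before W13D1 are 12 × 0.02 = 0.24 against 4 × 0.02 = 0.08. With equal risk per week, 3-weekly visits carry 6% and the arms match: 4 × 0.06 = 0.24. Other features do not settle the direction: home epoetin alfa doses have no hemoglobin check, and Table 5 has a cytopenia delay row that Table 7 lacks.

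**Conclusion.** The point holds as a minor one. Followed as written, the Table 3 note moves interim FACT-An and QLQ-C30 visits with dose delays, and the note and Section 6.4 disagree on whether quality of life is exempt. A questionnaire due during a delay can then be taken only when dosing resumes, and one visit label can cover study days that differ by the length of the delay. Section 9.10.1 states no calendar mapping.

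The day shifts rest on assumed delay lengths and a single delay starting at W7D1. The documents give no delay rates or durations, so neither the size nor the direction of a between-arm bias can be computed, and no point estimate of hidden difference is warranted.

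Nor do the documents support reading this as a threat to the trial's conclusions. Quality of life is outside the gate-keeping sequence in Section 9.7.2, and Section 9.10.1 calls its t-tests descriptive. The primary endpoint and Type I error are unaffected.

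**What to change.** 1. Reconcile the Table 3 note with Section 6.4, so that it is explicit whether quality-of-life questionnaires are exempt from dose delays.
2. Add a Table 3 footnote: interim FACT-An and QLQ-C30 are completed once, at their scheduled study day from first dose and within a stated window, regardless of dose delay. Examples are Days 43, 64, 85, 106, 127 and 148 for FACT-An, with the Week 2 to Week 4 visits treated the same way, and Days 43, 85 and 127 for QLQ-C30. Any contact or unscheduled visit inside the window will serve. They should not be repeated at every weekly recheck, which would sample delayed subjects more often than others.
3. State in Section 9.10.1, and carry into the HRQoL SAP, that the by-visit analysis uses study-day windows.

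The cost is a footnote, a sentence of analysis text and a few questionnaires completed outside dosing visits. No dosing or dose-delay rule changes.
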